SAMPLE SIZE CALCULATION	
For the aim of the sample size calculation, the safety profile of GGPSP will be compared to safety data reported in the scientific literature for the treatment of lower limb deformities by the means of guided growth performed by tension band plate. The sample size, therefore, was calculated estimating the required number of subjects so that the primary endpoint of the Study for GGPSP (i.e. percentage of subjects that experienced at least one complication as above described) ranges within the state-of-art safety profile of this treatment, that is, it is within the safety data reported in the literature for its previous version (the GGS) and for equivalent medical devices. Specifically, the scientific literature reports that the percentage of patients treated by a tension band plate for a lower limb deformity that faced at least one complication is between 3% and 12% depending on the many factors, mainly the diversity of the primary diagnosis. Assuming the expected percentage of patients with at least one complication for GGPSP will be 3%, 70 implants was calculated to be the sample size of this study so that the upper limit of the 95% confidence interval for the primary endpoint, based on the exact binomial method, is under 12%. Since each patient may have been treated for the correction of multiple localized deformities in different long bones, it is understood that each eligible subject may contribute to the data collection of multiple implants (average 2). For this reason, approximately 40 patients are expected to be enrolled.

2 Medical Device Information

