8.7 Number of Patients Expected to be Enrolled

The sample size was therefore calculated by estimating the number of implants required so that the confidence limits of the study's primary endpoint for the 8-Plate Plus (i.e., the percentage of subjects who experienced at least one complication certainly or possibly related to the investigational device, as described above) fall within the safety profile of the state of the art for this treatment, namely within the safety data reported in the literature for its predecessor (the GGS) and for other equivalent medical devices.

Specifically, the scientific literature reports that the percentage of patients treated with a tension band plate for a lower limb deformity who experienced at least one device-related complication ranges from 3% to 12%, depending on several factors, primarily the heterogeneity of the primary diagnosis [7].

Assuming that the expected percentage of patients with at least one complication certainly or possibly related to the device for the 8-Plate Plus will be 3%, the sample size calculation showed that, in order for the upper limit of the 95% confidence interval for the primary endpoint (calculated using the exact binomial method) to remain below 12% (i.e., 9.94%), 70 implants are required.

As each patient may have been treated for the correction of multiple deformities located in different long bones, it is understood that each eligible subject may contribute data for more than one implant (on average 2). For this reason, approximately 40 patients are expected to be enrolled.

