The safety profile of the 8-Plate Plus, as measured in the present Clinical Investigation, will be compared with the safety data reported in the scientific literature for the treatment of lower limb deformities by guided growth performed with equivalent tension-band plates.

The sample size calculation was performed in order to estimate the confidence intervals for the primary endpoint (safety outcome related to treatment response) of the 8-Plate Plus and to enable a reliable comparison with the data reported in the literature.

Accordingly, the sample size was determined by estimating the number of implants required so that the confidence intervals for the study primary endpoint with the 8-Plate Plus would fall within the established safety profile for this treatment, namely within the range of safety data reported in the literature for its predecessor (the GGS) and for equivalent medical devices.

Specifically, the scientific literature indicates that the proportion of patients treated with a tension-band plate for lower limb deformity who experience at least one device-related complication ranges between 3% and 12%, depending mainly on the heterogeneity of the underlying diagnosis.

Assuming that the expected proportion of patients experiencing at least one complication with the 8-Plate Plus is 3%, the sample size calculation showed that, in order for the upper limit of the 95% confidence interval for the primary endpoint (calculated using the exact binomial method) to remain below 12% (i.e., 9.94%), a total of 70 implants (in approximately 40 patients) are required.

The clinical data collected during the present Clinical Investigation will be analysed using descriptive statistics:

- the primary endpoint will be presented as a percentage value with its corresponding 95% confidence interval;
- the secondary endpoint will be presented as a percentage value with its corresponding 95% confidence interval.

The clinical data obtained from this Clinical Investigation will be used to complete the evaluation of the clinical performance and safety of the 8-Plate Plus, with the objective of confirming that the device can be considered safe and effective as hypothesised during its development, based on the preclinical evaluations conducted for CE marking.

17 Publication of Results

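### Sections 8.7 and 16 say the sample size puts the confidence limits inside the 3–12% literature range. No result at the planned sizes does so; the calculation supports only an upper limit below 12%, on implants rather than subjects.

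*Combined protocol and SAP*

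**What the plan says.** Section 16 (Statistics) explains the number of implants by an aim for the interval: that "the confidence intervals for the study primary endpoint with the 8-Plate Plus would fall within the established safety profile for this treatment". The sentence goes on to equate this profile with the range of published safety results for the earlier version of the device and for comparable devices. The next paragraph puts numbers on the range: the literature proportion "ranges between 3% and 12%, depending mainly on the heterogeneity of the underlying diagnosis". Section 8.7 has a parallel sentence, in which the confidence limits of the primary endpoint are to "fall within the safety profile of the state of the art for this treatment".

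Both sections then give the calculation. The expected proportion is taken as 3%, and the exact binomial upper 95% limit is required "to remain below 12% (i.e., 9.94%), a total of 70 implants (in approximately 40 patients) are required". No lower limit is reported anywhere. The synopsis gives the same upper-limit condition. Its introductory phrase, "ranges within the state-of-art safety profile of this treatment", refers to the endpoint percentage rather than to an interval.

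The primary endpoint (synopsis and section 8.4) is the percentage of subjects with at least one complication. Section 8.7 assumes an average of 2 implants per subject.

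**The concern.** The introductory sentences describe a two-sided property: an interval lying inside a range with two ends. The calculation that follows controls only one end. The assumed rate, 3%, is also the bottom of the range. An exact interval always contains the observed proportion, so an interval around an observed 3% must reach below 3% at any sample size. The stated reason and the calculation therefore cannot describe the same thing.

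A second gap becomes visible once the aim is reduced to the upper limit. The 9.94% is given for the primary endpoint, whose denominator is subjects, but it is computed on 70 implants. A reader of section 16 would expect the reported interval to end near 10% if the device behaves as assumed. On the endpoint's own denominator it would not, unless no subject has an event.

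**Working it through.** **Inputs.** Range 3% to 12% (8.7, 16). Expected proportion 3% (8.7, 16, synopsis). Exact binomial 95% interval (8.7, 16, synopsis). 70 implants in about 40 patients (16), average 2 implants per patient (8.7). Hence 70 implants correspond to 70/2 = 35 subjects, and 40 subjects to 40 × 2 = 80 implants. All four sizes are checked.

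**Formula.** For x events in n units, the two-sided 95% Clopper-Pearson limits are: lower = 0.025 quantile of Beta(x, n − x + 1), upper = 0.975 quantile of Beta(x + 1, n − x). For x = 0 the lower limit is 0 and the upper is 1 − 0.025^(1/n).

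**The plan's figure.** 70 × 0.03 = 2.1, nearest whole count 2. For 2/70 (2.86%) the interval is 0.35% to 9.94%. The stated 9.94% reproduces, which also shows that the limit is two-sided and that 2 whole events were used (2.1 unrounded would give 10.16%). The lower limit of this same interval, 0.35%, is below 3%.

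**Can any result lie inside 3–12%?** Both limits rise with x, so it is enough to find the largest count with an upper limit below 12% and the smallest count with a lower limit of at least 3%.

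| n | Largest x with upper < 12% | Next count | Smallest x with lower ≥ 3% |
|---|---|---|---|
| 70 implants | 2 (0.35–9.94%) | 3 (0.89–12.02%) | 6 (3.21–17.73%) |
| 80 implants | 3 (0.78–10.57%) | 4 (1.38–12.31%) | 7 (3.59–17.20%) |
| 40 subjects | 0 (0–8.81%) | 1 (0.06–13.16%) | 5 (4.19–26.80%) |
| 35 subjects | 0 (0–10.00%) | 1 (0.07–14.92%) | 4 (3.20–26.74%) |

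In every row the count needed for the lower limit is above the largest count allowed by the upper limit, so no result qualifies. Wilson, Jeffreys and Wald 95% intervals also give no qualifying count at any of the four sizes.

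**Would a larger sample help?** Not at the plan's assumed rate. With 3% observed, the exact lower limit is 0.62% for 3/100, 1.11% for 6/200, 2.03% for 30/1000 and 2.67% for 300/10000. The smallest n at which any count at all fits is 139, and that needs 9 events (6.5%; 3.003% to 11.94%), about twice the assumed rate.

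**The upper-limit aim on the endpoint's own unit.** Expected events at 3% are 40 × 0.03 = 1.2, or 35 × 0.03 = 1.05. The nearest whole count, as the plan itself used, is 1 in both cases. The upper limits are then 13.16% (1/40) and 14.92% (1/35), both above 12%. Only 0 events meets the aim. As context, the chance of 0 events in 40 at a true 3% is 0.97^40 = 0.296. The plan states no such chance, so this contradicts nothing in it.

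**The case against.** The strongest reply is that the plan resolves its own loose sentence. In 8.7 and 16 the range statement is an introduction; the aim that follows is explicit, one-sided and numeric, and it also appears in the synopsis. For a complication rate, being within the state of the art naturally means being no worse than it. The 3% is the low end of published rates and not a floor to be kept above. The calculation is expressly conditional on 3%, the analysis is descriptive, and nothing in the sample size or the reported interval depends on the introductory wording.

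Most of this stands. It shows that the operative aim is sensible and that little turns on the introductory sentences. It does not make those sentences true: 8.7 speaks of limits in the plural, and 16 speaks of intervals lying within a range to which it then gives two ends.

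Three stronger readings are tempting and are not supported:

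- A reader might infer that the sample size arithmetic is wrong. It is not; 9.94% is exact for 2/70.
- A reader might infer that the plan has no valid reason for its size, or that the study is too small. The upper-limit reason is also stated and is true for 2 events in 70 units, and no power or probability of success is claimed.
- A reader might infer that the synopsis makes the same false statement. Its phrase describes the endpoint percentage, not an interval.

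The unit question is a different issue from the range wording. It belongs here only because the upper-limit aim, once it stands alone, is attributed to a subject-level endpoint that the 9.94% does not describe.

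**Conclusion.** The statements in 8.7 and 16 are wrong as written, with limited consequence. The chosen size does not place the confidence limits inside 3–12%: no event count does so at 70 or 80 implants or at 35 or 40 subjects, and the plan's own expected result gives 0.35% to 9.94%.

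What the calculation does support is an upper limit below 12% with at most 2 events in 70 implants, provided implants in the same subject are treated as independent. It does not support that limit for the primary endpoint, where one affected subject among 35 to 40 is enough to pass 12%.

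The conclusion rests on the two-sided exact interval, which the 9.94% confirms, and on the plan's own figures of about 40 patients and 2 implants each. A lower limit below 3% is not a safety problem, and the planned descriptive reporting remains valid.

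**What to change.** 1. In 8.7 and 16, replace the sentences about falling within the range with: *The upper limit of the two-sided exact 95% CI is below 12% if no more than 2 events are seen in 70 implants (9.94% at 2 events), treating implants in the same subject as independent.*

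2. Beside it, add: *The 9.94% does not apply to the subject-level primary endpoint. At about 35 to 40 subjects, the upper limit is below 12% only with 0 events (0/35 gives 10.00%, 0/40 gives 8.81%; 1/35 gives 14.92%, 1/40 gives 13.16%).*

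The range of subjects is kept because the plan gives only an approximate number. The analysis stays descriptive as planned. No larger sample, decision rule or probability of success needs to be written in.

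The cost is a less favourable stated precision for the primary endpoint and an amendment to be classified under section 14. If the amendment is judged substantial, that section suspends the investigation until the ethics committee gives a new favourable opinion.
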